8.6.6 Adverse Events Based on Signs and Symptoms

All AEs spontaneously reported by the subject or reported in response to the open question from the study site staff: *'Have you had any health problems since the previous visit/you were last asked?'*, or revealed by observation will be collected and recorded in the eCRF. When collecting AEs, the recording of diagnoses is preferred (when possible) to recording a list of signs and symptoms. However, if a diagnosis is known and there are other signs or symptoms that are not generally part of the diagnosis, the diagnosis and each sign or symptom will be recorded separately.

8.6.7 Adverse Events Based on Examinations and Tests

The results from the protocol-mandated laboratory tests and vital signs will be summarised in the Clinical Study Report. Deterioration as compared to baseline in protocol-mandated procedures (eg, safety laboratory tests and vital signs) should therefore only be reported as AEs if they fulfil any of the SAE criteria or are the reason for discontinuation of treatment with the investigational product.

If deterioration in a laboratory value/vital sign is associated with clinical signs and symptoms, the sign or symptom will be reported as an AE and the associated laboratory result/vital sign will be considered as additional information. Wherever possible the reporting Investigator uses the clinical, rather than the laboratory term (eg, anemia versus low hemoglobin value). In the absence of clinical signs or symptoms, clinically relevant deteriorations in non-mandated parameters should be reported as AE(s).

Deterioration of a laboratory value, which is unequivocally due to disease progression, should not be reported as an AE/SAE.

Any new or aggravated clinically relevant abnormal medical finding at a physical examination as compared with the baseline assessment will be reported as an AE unless unequivocally related to the disease under study, see Section 8.6.9 and Section 8.6.10.

8.6.8 Hy's Law

Cases where a subject shows elevations in liver biochemistry may require further evaluation, and occurrences of AST or ALT $\geq 3 \times ULN$ together with total bilirubin $\geq 2 \times ULN$ may need to be reported as SAEs. Please refer to Appendix D for further instruction on cases of increases in liver biochemistry and evaluation of Hy's law.

8.6.9 Disease Under Study

Systemic symptoms of the disease under study are those which might be expected to occur as a direct result of the clinical presentation associated with COVID-19 pneumonia and respiratory illness. Events which are unequivocally due to disease under study should not be reported as an AE during the study unless they meet SAE criteria or lead to discontinuation of the investigational product.

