6. STUDY TREATMENTS

Study treatment is defined as any investigational product(s) (including marketed product comparator and placebo) or medical device(s) intended to be administered to a study subject according to the study protocol. Study treatment in this study refers to acalabrutinib.

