8.6 Collection of Adverse Events

The Principal Investigator is responsible for ensuring that all staff involved in the study are familiar with the content of this section.

The definitions of an AE or SAE can be found in Appendix B.

The following are NOT considered an AE:

- **Pre-existing condition that has not worsened:** A pre-existing condition (documented on the medical history eCRF) is not considered an AE unless the severity, frequency, or character of the event worsens during the study period.
- **Diagnostic testing and procedures:** Testing and procedures should not be reported as AEs or SAEs, but rather the cause for the test or procedure should be reported. If a test or procedure is done to rule out a diagnosis, the sign or symptom leading to the test/procedure should be the event term, and the event term should only be updated to the diagnosis if/when the diagnosis is confirmed. Testing and procedures performed solely as screening measures (eg, routine screening mammography or colonoscopy) should not be reported as AEs or SAEs.
- Abnormal laboratory results: Abnormal laboratory results are not AEs unless they are clinically significant. For example, a clinically significant laboratory result is one that requires treatment (for example a blood transfusion for low haemoglobin) or requires a change in study drug (eg, lowering the dose or withholding study drug while the laboratory finding resolves or stabilizes).
- **Progression of underlying disease:** Progression of underlying disease unequivocally related to COVID-19 pneumonia (such as worsening of respiratory status or complications associated with pneumonia) will not be reported as an AE if it is clearly consistent with the suspected progression of the underlying disease. Clinical symptoms of progression may be reported as AEs if the symptoms cannot be determined as exclusively due to the progression of the underlying disease, or if they do not fit the expected pattern of progression for the disease under study.

Symptomatic deterioration may occur in some subjects. Symptomatic deterioration is when progression is evident in the subject's clinical symptoms and the Investigator may elect not to perform further disease assessments.

If there is any uncertainty about an AE being due only to the disease under study, it should be reported as an AE or SAE.

AE will be reported by the subject (or, when appropriate, by a caregiver, surrogate, or the subject's legally authorized representative).

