3.2.1 Adverse events

After the signing of the ICF, all SAEs must be reported. After the first dose of study treatment, all AEs/SAEs, irrespective of attribution of causality, must be reported. AE reporting, irrespective of seriousness, ends 28 (± 3) days after the last dose of study treatments(s) for those on acalabrutinib + BSC (Arm 1) and 38 (± 3) days from randomization for those on BSC only (Arm 2).

The following are NOT considered an AE:

- **Pre-existing condition that has not worsened:** A pre-existing condition (documented on the medical history eCRF) is not considered an AE unless the severity, frequency, or character of the event worsens during the study period.
- **Diagnostic testing and procedures:** Testing and procedures should not be reported as AEs or SAEs, but rather the cause for the test or procedure should be reported. If a test or procedure is done to rule out a diagnosis, the sign or symptom leading to the test/procedure should be the event term, and the event term should only be updated to the diagnosis if/when the diagnosis is confirmed. Testing and procedures performed solely as screening measures (e.g., routine screening mammography or colonoscopy) should not be reported as AEs or SAEs.
- **Abnormal laboratory results:** Abnormal laboratory results are not AEs unless they are clinically significant. For example, a clinically significant laboratory result is one that requires treatment (for example a blood transfusion for low haemoglobin) or requires a change in study drug (e.g., lowering the dose or withholding study drug while the laboratory finding resolves or stabilizes).
- **Progression of underlying disease:** Progression of underlying disease unequivocally related to COVID-19 pneumonia (such as worsening of respiratory status or complications associated with pneumonia) will not be reported as an AE if it is clearly consistent with the suspected progression of the underlying disease. Clinical symptoms of progression may be reported as AEs if the symptoms cannot be determined as exclusively due to the progression of the underlying disease, or if

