4.4.1 Adverse events

Verbatim descriptions of AEs will be mapped per version 23.0 of the MedDRA thesaurus terms and graded per National Cancer Institute (NCI) CTCAE, v5.0 or higher. Unless stated otherwise, only treatment-emergent adverse events (TEAEs) will be presented in the summaries. For acalabrutinib + BSC subjects, TEAEs are AEs starting or ongoing AEs worsening after the first dose of study treatment and AEs with start date up to the last dose of study treatment plus 28 (±3) days; for BSC only subjects, TEAEs are AEs starting or ongoing AEs worsening after date of randomization and AEs with start date up to 38 (± 3) days after randomization. In the case a subject's actual treatment received is different than their randomized treatment, TEAEs are AEs starting on or after the date of randomization up to the later of 38 (± 3) days after randomization or the last dose of study treatment plus 28 (±3) days. When programmatically assigning the AEs as treatment emergent, the upper window will be used.

The following summaries will be provided:

- A summary of the number and percentage of subjects reporting any TEAE, TEAEs with outcome of death, at least one TEAE of CTCAE grade 3 or higher, at least one serious TEAE, at least one TEAE possibly related to study drug, and at least one TEAE leading to discontinuation of study drug by treatment group.
- A summary of the number of TEAEs, TEAEs with outcome of deaths, TEAEs with CTCAE grade 3 or higher, serious TEAEs, TEAEs possibly related to study drug, and TEAEs leading to discontinuation of study drug by treatment group.
- A summary of the number and percentage of subjects reporting a TEAE by treatment group, SOC and PT.
- A summary of the number and percentage of subjects reporting the most common TEAEs (occurring in at least 5% of overall subjects) by treatment group, SOC and PT.
- A summary of the number and percentage of subjects reporting a TEAE by treatment group, CTCAE grade, SOC and PT. This will include a subset of grade 3 or higher.
- A summary of the number and percentage of subjects reporting a TEAE possibly related to study drug by SOC and PT.
- A summary of the number and percentage of subjects reporting a TEAE leading to discontinuation of study drug by SOC and PT.

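### AE reporting that depends on stopping acalabrutinib can add a few non-serious laboratory and vital-sign TEAEs to Arm 1 that cannot arise under BSC

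*Protocol*

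**What the plan says.** Protocol 8.6.7 says that deterioration from baseline in protocol-mandated procedures, such as safety laboratory tests and vital signs, should "only be reported as AEs if they fulfil any of the SAE criteria or are the reason for discontinuation of treatment with the investigational product". Protocol 8.6.9 says that events clearly caused by COVID-19 "should not be reported as an AE during the study unless they meet SAE criteria or lead to discontinuation of the investigational product". Protocol 8.6.10 covers worsening attributable to COVID-19 pneumonia and bars it from AE and SAE reporting, with no exception for seriousness or discontinuation.

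Protocol 8.6 adds that an abnormal laboratory result is an AE only if clinically significant. It gives two examples: the result needs treatment, or it "requires a change in study drug (eg, lowering the dose or withholding study drug while the laboratory finding resolves or stabilizes". SAP 3.2.1 repeats this.

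Protocol section 6 states: "Study treatment in this study refers to acalabrutinib". Arm 2 is BSC alone (4.1) in an open-label design (6.3).

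Safety is a primary objective. The tables in SAP 4.4.1 include "A summary of the number and percentage of subjects reporting a TEAE by treatment group, SOC and PT", and SAP 4.4.1.1 summarizes events of clinical interest by treatment group as well.

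**The concern.** A reporting rule should treat the two arms alike if their AE counts are to be set side by side. Here one of the two conditions that turn a non-serious finding into an AE is an action on a drug that only one arm receives. With equal true rates of the finding, the acalabrutinib column can collect reports and the BSC column cannot. The direction is fixed, towards apparent harm from acalabrutinib.

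The findings most open to this are ones a reader would readily attribute to the drug. Protocol 6.7 links unresolved Grade 4 neutrophil or platelet decreases to discontinuation, and Table 5 lists neutropenia and thrombocytopenia as acalabrutinib risks.

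**Working it through.** The plan states no figure on this point, so there is none to reproduce. The check is a reading of the rules, followed by simple arithmetic on size.

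**1. Who can meet the discontinuation condition.** Only someone who has taken acalabrutinib. The safety analysis set counts any subject with at least one dose as acalabrutinib-treated (SAP 2.1.3), so its BSC column holds only subjects for whom the condition can never be met.

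**2. Which events depend on that condition alone.**

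| Event | Acalabrutinib-treated | BSC only |
|---|---|---|
| Serious laboratory or vital-sign deterioration | AE | AE |
| Laboratory or vital-sign change with signs or symptoms (8.6.7) | Sign or symptom reported | Sign or symptom reported |
| Attribution to COVID-19 uncertain (8.6) | AE | AE |
| Laboratory result that needed treatment (8.6) | AE | AE |
| Non-serious, symptom-free, untreated change in a mandated test; drug stopped if there is one | AE (8.6.7) | Not an AE |
| Non-serious event clearly due to COVID-19; drug stopped if there is one | AE under 8.6.9; not under 8.6.10 | Not an AE under either |

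Only the last two rows differ between arms. The last row differs only if 8.6.9 governs. The row above it differs whichever of those two sections governs.

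**3. How such an event reaches the tables.** An AE starting after first dose and within the reporting period is a TEAE in Arm 1 (Protocol 9.6.1, SAP 4.4.1), so it enters the by-arm TEAE tables. The event-of-clinical-interest tables can inherit it, because the neutropenia category in SAP 8.1 includes the preferred term for a decreased neutrophil count.

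**4. Whether the plan offsets it.** Haematology and chemistry are sampled on the same in-hospital, Day 10, Day 14 and Day 28 schedule in both arms (Protocol Tables 1 and 2), and values are CTC-graded (SAP 3.2.3). The definite by-arm summaries in SAP 4.4.3 cover CRP, lymphocytes, ferritin, fibrinogen, PT, aPTT, INR, D-dimer, procalcitonin and troponin, plus Hy's law and uric acid. Neutrophils, platelets and the individual transaminases are not among them. Haematology and chemistry get by-subject listings, and shift tables are optional. Vital signs are summarized by arm as a definite output (SAP 4.4.4).

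**5. Size.** Let q be the true proportion of subjects with a qualifying event, equal in both arms, and s the share of those events that stop acalabrutinib. The expected excess is q × s in Arm 1 against 0 under BSC. The documents give neither q nor s. Purely as assumptions:

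- q = 20%, s = 10%: 0.20 × 0.10 = 2%, or 30 × 0.02 = 0.6 subjects. The chance of at least one such report is 1 − 0.98^30 = 0.455.
- q = 60%, s = 50%: 0.60 × 0.50 = 30%, or 9 of 30 subjects.

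The upper end is arithmetic only; nothing in the documents makes it plausible for so narrow a class. What is certain is the weight of one report: 1/30 = 3.3 points. The common-TEAE table uses a 5% cut-off over all subjects: 0.05 × 60 = 3 subjects with the same preferred term, or 0.05 × 62 = 3.1, hence 4, at the 62 randomized (SAP 1.3).

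**The case against.** The case against is strong on scope.

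- Most AEs are reported in both arms from randomization (8.6.2), and the table above shows how little is left.
- That remainder may be almost empty. An unresolved Grade 4 cytopenia may be judged serious as an important medical event, and if treated it is an AE in either arm under 8.6. Most other triggers in Protocol 6.7 are clinical events.
- A COVID-19 event would have to stop the drug and still be non-serious. Respiratory failure does not by itself require stopping (6.1.3.2), and inability to swallow is a discontinuation reason separate from AE (7.1).
- Laboratory data are a named part of the primary safety endpoint, and safety is descriptive, without tests (SAP 4.4).
- AEs leading to discontinuation have their own table, and the listings give seriousness and action taken, so a careful reader could find the affected events.

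All of this stands as a limit on size. It does not remove the asymmetry in 8.6.7, and the listings do not replace a by-arm comparison of neutrophils, platelets and transaminases.

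A reader might also infer that dose holds or changes open a third one-sided route, from the 8.6 wording on a result that "requires a change in study drug". The documents do not support that as a separate threshold. The test there is clinical significance, which applies to both arms, and the drug change is one example beside the need for treatment.

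**Conclusion.** The point holds for a narrow class: non-serious, symptom-free, untreated deterioration in a mandated laboratory test or vital sign that leads to stopping acalabrutinib and, if 8.6.9 rather than 8.6.10 governs, non-serious events clearly due to COVID-19 that do the same. The effect can only add reports to the acalabrutinib column. Its size is unknown and probably small, at about 3.3 points per subject with 30 per arm. The conclusion assumes that sites apply 8.6.7 as written.

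Two stronger readings are tempting and not supported:

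- A reader might infer that any non-serious event is reportable in Arm 1 only. Most are reportable in both arms.
- A reader might put the artefact at 3 against 0 subjects, from the 10% implied by the 90% success assumption in Protocol 9.2, or at 6 against 0, from the 20% discontinuation rate that prompts a safety review in 4.4. The first is an efficacy failure rate. The second counts toxicity attributed to acalabrutinib, which excludes events due beyond doubt to COVID-19 and includes serious, symptomatic and treated events that are reportable in both arms. Neither measures this class.

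This is a cheap improvement, not a defect that undermines the safety analysis.

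**What to change.** 1. **Leave the discontinuation condition and the main TEAE tables as they are.** AEs leading to discontinuation are part of the primary safety endpoint, and removing the condition could lose some of them. Recruitment was complete when SAP version 3.0 was written, so the useful change is in the analysis.

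2. **SAP 4.4.1: add one supplementary by-arm TEAE table.** It omits only AEs that meet all four criteria: non-serious; action taken was drug withdrawn; no treatment given for the AE; and a mandated laboratory or vital-sign term. The first three are AE fields in Protocol 8.6.4, and the fourth follows from the coded term. The omitted events stay in the discontinuation table. The no-treatment criterion matters: without it, treated laboratory AEs would leave Arm 1 but stay under BSC, and the bias would reverse.

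3. **SAP 4.4.3: make the by-arm CTC-grade shift tables definite** for haematology, including neutrophils and platelets, and for liver chemistry. The arms are then compared on data collected in the same way.

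4. **Reconcile Protocol 8.6.9 and 8.6.10.** Protocol 8.6.4 lists no AE field for events due to the disease under study, so the supplementary table cannot remove that class by program. If 8.6.9 governs, the text should say that those reports remain.

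The cost is a few extra tables from data already planned for collection.

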8.6.10 Disease Progression

Disease progression can be considered as a worsening of a subject's condition attributable to COVID-19 pneumonia for which the investigational product is being studied. It may be an increase in the severity of the disease under study and/or increases in the symptoms of the disease. Events, which are unequivocally due to COVID-19 pneumonia, should not be reported as an AE or SAE during the study. Events attributable to disease progression of COVID-19 include pulmonary failure, ARDS, sepsis, shock, multiorgan failure and death.

8.6.11 Deaths

All deaths that occur during the study treatment period, or within the protocol-defined follow up period after the administration of the last dose of study treatment, must be reported as follows:

- Death clearly resulting from disease progression should be documented in the eCRF in the Death page. It should not be reported as an SAE.
- Where death is not due (or not clearly due) to progression of the disease under study, the AE causing the death must be reported as an SAE within 24 hours. It should also be documented in the Death page in the eCRF. The report should contain a comment regarding the co-involvement of disease progression, if appropriate, and should assign the main and contributory causes of death.
- Deaths with an unknown cause should always be reported as an SAE and documented in the Death page in the eCRF, but every effort should be made to determine a cause of death. A post-mortem may be helpful in the assessment of the cause of death, and if performed, a copy of the post-mortem results should be forwarded to Sponsor Patient Safety or its representative within the usual time frames.

Deaths occurring after the protocol-defined follow-up period after the administration of the last dose of study treatment should be documented in the Death page. If the death occurred as a result of an event that started after the defined follow-up period and the event is considered to be due to a late-onset toxicity to study treatment, then it should also be reported as an SAE.

8.6.12 Adverse Events of Special Interest

AESIs are events of scientific and medical interest specific to the further understanding of the acalabrutinib safety profile and require close monitoring and rapid communication by the

Investigators to the Sponsor. An AESI can be serious or non-serious. All AESIs will be recorded in the eCRF. Serious AESIs will be recorded and reported as per Section 8.7.1.

The following events are AESIs for subjects receiving acalabrutinib and must be reported to the Sponsor expeditiously (see Section 8.7.1 for reporting instructions), irrespective of regulatory seriousness criteria or causality:

• Ventricular arrhythmias (eg, ventricular extrasystoles, ventricular tachycardia, ventricular arrhythmia, ventricular fibrillation)

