8.1.5 Physical Examinations and Chest Imaging, Electrocardiogram, and Echocardiogram

The screening physical examination will be symptom-directed and include height, weight and lung auscultation.

Per standard of care, chest imaging can be done by chest x-ray or CT scan with contrast, or any other appropriate means to confirm pneumonia prior to or upon hospitalization (within 7 days of randomization). Post treatment assessment will continue as clinically indicated.

A single 12-lead ECG and will be done during the screening period and at Day 10 or upon discharge from the hospital. ECG should be collected during the treatment period, as clinically

indicated. For all ECGs, details of rhythm, ECG intervals, and an overall evaluation will be recorded.

An echocardiogram should be collected at baseline or during the treatment period, as clinically indicated per SoA. Percentage left ventricular ejection fraction should be recorded.

If the Investigator considers an abnormal ECG or echocardiogram finding at screening or baseline to be clinically significant, that finding should be reported as a concurrent condition.

Any clinically significant abnormal ECG or echocardiogram findings during the treatment period should be recorded in the source document and the AE section of eCRF, according to standard AE collection and reporting processes.

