8.6.2 Time Period and Frequency for Collecting AE and SAE Information

After the signing of the ICF, all SAEs must be reported. After randomization, all AEs/SAEs, irrespective of attribution of causality, must be reported.

AE reporting, irrespective of seriousness, ends 28 (\pm 3) days after the last dose of study treatments(s) for those on acalabrutinib + BSC (Arm 1) and 38 (\pm 3) days from randomization for those on BSC only (Arm 2).

SAEs considered related to study treatments(s) or study procedures occurring after the end of the AE reporting period (as defined above) must be reported. Information on concomitant medications at the time of the treatment-related SAE will also be collected.

All SAEs will be recorded and reported to the Sponsor or designee within 1 day (ie, immediately but **no later than 24 hours** from when he or she becomes aware of it), as indicated in Appendix B. The Investigator will submit any updated SAE data to the Sponsor within 24 hours of it being available.

The method of recording, evaluating, and assessing causality of AE and SAE and the procedures for reporting SAEs are provided in Section 8.7.1.

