4.4.1.1 Deaths, serious adverse events (SAEs), and other significant adverse events

The following summaries will be provided:

- A summary of the number and percentage of total deaths, deaths related to the disease under investigation (as determined by the investigator), deaths after the end of safety follow-up (28 (\pm 3) days after last dose for acalabrutinib + BSC subjects, 38 (\pm 3) days after randomization for BSC only subjects) by treatment group

- A summary of the number and percentage of subjects reporting a treatment-emergent SAE by treatment group, SOC and PT.
- A summary of the number of treatment-emergent SAEs by treatment group, SOC and PT.
- A summary of the number and percentage of subjects reporting a treatment-emergent SAE leading to discontinuation of study drug by SOC and PT.
- A summary of the number and percentage of subjects with a treatment-emergent SAE with an outcome of death by treatment group and PT.

Adverse events of special interest (AESI) for acalabrutinib include ventricular arrhythmias (e.g., ventricular extrasystoles, ventricular tachycardia, ventricular arrhythmia, ventricular fibrillation). AESI PTs are listed in Section 8.1. These events will be summarized as follows:

- A summary of the number and percentage of subjects reporting an AESI by treatment group, CTCAE grade, group term and PT.
- A summary of the number and percentage of subjects reporting an AESI possibly related to study drug by group term and PT.
- A summary of the number and percentage of subjects reporting an AESI leading to discontinuation of study drug by SOC and PT.

A list of AESI PTs will also be provided.

Events of clinical interest (ECIs) are provided in Section 8.1. ECIs will be reported for the duration of study treatment and during any protocol-specified follow-up period. These events will be summarized similarly to AESIs by treatment group and a list of ECI PTs will be provided.

The following by-subject listings will be presented:

- A by-subject listing of key information for serious adverse events (SAEs).
- A by-subject listing of key information for AESIs and ECIs.
- A by-subject listing of deaths, including the date of death, the primary and secondary cause of death, whether an autopsy was performed and whether the death was related to the disease under study.
- A by-subject listing of key information for AEs leading to discontinuation of study treatment.

The following subject narratives will be provided:

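### Ventricular arrhythmias must be recorded irrespective of seriousness or causality only in acalabrutinib recipients, which may bias the by-arm AESI table for low-grade events

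*Protocol*

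**What the plan says.** **AESI rule.** Protocol 8.6.12 lists ventricular arrhythmias, with ventricular extrasystoles among the examples, and states: "The following events are AESIs for subjects receiving acalabrutinib and must be reported to the Sponsor expeditiously". The duty applies "irrespective of regulatory seriousness criteria or causality", and the section requires every AESI to be entered in the eCRF. It gives no counterpart for subjects on BSC alone.

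**General AE rule.** Protocol 8.6.2 covers both arms: "After randomization, all AEs/SAEs, irrespective of attribution of causality, must be reported". SAP 3.2.1 sets a different start: "After the first dose of study treatment, all AEs/SAEs, irrespective of attribution of causality, must be reported". Protocol Section 6 says "Study treatment in this study refers to acalabrutinib", so a BSC subject never reaches that start.

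**Filters that can keep a non-serious finding off the AE page.**
- Protocol 8.6.7: deteriorations in protocol-mandated procedures "should therefore only be reported as AEs if they fulfil any of the SAE criteria or are the reason for discontinuation of treatment". The treatment meant there is the investigational product.
- Protocol 8.6.9: events unequivocally due to the disease under study are not AEs unless they are serious or lead to stopping the investigational product.
- Protocol 8.1.5: what goes to the AE page is "Any clinically significant abnormal ECG or echocardiogram findings during the treatment" period. This is a judgement of clinical significance, and neither arm is named. SAP 3.2.4 is similar but replaces clinical significance with an exception for findings unequivocally related to the disease.

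**Planned output.** SAP 4.4.1.1 specifies "A summary of the number and percentage of subjects reporting an AESI by treatment group, CTCAE grade, group term and PT". SAP 8.1 identifies AESIs by a list of preferred terms that includes ventricular extrasystoles and has no restriction by arm. SAP 4.4.1.1 plans no formal test of AE rates.

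**The concern.** Safety is a primary objective, this is its only named AESI, and BSC is the only concurrent comparator. For a subject on acalabrutinib, a run of extrasystoles must be recorded whatever its seriousness or cause. For a subject on BSC, site staff who know the allocation may judge the same finding not clinically significant or due to COVID-19, and leave it off the AE page.

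The mildest events could then be solicited in one arm and left to discretion in the other. The by-arm table would mix any drug effect with a difference in recording. A descriptive table is still read side by side, so the absence of a test does not remove the problem.

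**Working it through.** **Step 1. Follow one non-serious ventricular finding through the rules in each arm.**

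| Rule | Acalabrutinib recipient | BSC only |
|---|---|---|
| AESI duty (Protocol 8.6.12) | Recorded, whatever its seriousness or cause | Does not apply |
| All AEs after randomization (8.6.2) | Applies | Applies |
| ECG findings (8.1.5) | AESI duty appears to override the clinical-significance filter | Recorded if judged clinically significant |
| Due to the disease (8.6.9) | Appears overridden, since the AESI duty ignores causality | Not an AE if non-serious and unequivocally due to COVID-19 |
| Mandated procedures (8.6.7) | Appears overridden | If applied to ECG, an AE only if serious; the discontinuation route cannot occur |

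The arms differ where a filter operates in BSC and is overridden for acalabrutinib recipients. That leaves non-serious findings judged not clinically significant, judged unequivocally due to COVID-19, or handled under 8.6.7. Serious events are reportable in both arms.

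**Step 2. Separate recording from timing.** The AESI table counts events that were recorded and coded to a listed term. How quickly the sponsor is told does not change the count.

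**Step 3. Illustrate the size.** The documents give no ventricular arrhythmia rate and no capture rate, so there is no figure of the plan's own to reproduce. Inputs:
- 30 subjects per arm, the planned number (Protocol 9.2)
- equal true risk r in both arms (assumed)
- capture of 1 in Arm 1 (assumed)
- capture c in BSC (assumed)

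Expected counts are 30 × r in Arm 1 and 30 × r × c in BSC. The spurious difference is r × (1 − c). The last column is the exact binomial probability that Arm 1 shows strictly more AESI subjects than BSC.

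| r | c | Arm 1 | BSC | Spurious difference | P(Arm 1 > BSC) |
|---|---|---|---|---|---|
| 3% | 50% | 0.9 | 0.45 | 1.5 points | 0.45 |
| 5% | 50% | 1.5 | 0.75 | 2.5 points | 0.56 |
| 10% | 100% | 3.0 | 3.0 | 0 | 0.41 |
| 10% | 80% | 3.0 | 2.4 | 2 points | 0.52 |
| 10% | 50% | 3.0 | 1.5 | 5 points | 0.69 |
| 20% | 80% | 6.0 | 4.8 | 4 points | 0.59 |
| 20% | 50% | 6.0 | 3.0 | 10 points | 0.82 |

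For example, 10% × (1 − 0.5) = 5 points, or 30 × 0.05 = 1.5 subjects.

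**Step 4. Under one recording rule.** With equal capture (c = 1), r × (1 − 1) = 0 at any true risk.

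**The case against.** A reader might infer that such findings are often not AEs in BSC. The documents do not support that:
- Protocol 8.6.2 requires all AEs in both arms from randomization, and the reporting windows are comparable: 28 days after the last dose in Arm 1 (10 + 28 = 38 days on schedule) and 38 days from randomization in Arm 2.
- Protocol 8.6.6 adds events revealed by observation.
- Protocol 8.1.5 and SAP 3.2.4 name no arm, and the ECG schedule is the same in both.
- Any BSC event coded to a listed term enters the AESI table.

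The reach of 8.6.7 is also limited. Its examples are laboratory tests and vital signs, although they are only examples. It asks for clinically relevant deteriorations in non-mandated parameters to be reported. Only one post-baseline ECG is scheduled outright, at Day 10 or discharge, and 8.1.5 is the more specific ECG rule.

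Nor is it established that BSC has no treatment period. Protocol 9.3 counts BSC only as a treatment, and 9.6.1 gives Arm 2 its own treatment-emergent window. The term is ambiguous for BSC, which does not prove that findings go unrecorded.

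It would also be too strong to say that a true signal cannot be told from an artefact. The CTCAE-grade table lets low-grade events be set apart, and the by-subject ECG listings in SAP 4.4.5 do not depend on AE reporting. These allow a partial check.

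All of this stands, and it narrows the point. None of it gives BSC subjects the override that 8.6.12 gives acalabrutinib recipients.

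**Conclusion.** The concern holds in limited form. A stated rule, not merely missing detail, permits unequal recording of non-serious ventricular arrhythmias. Because the SAP tabulates AESIs by arm in an open-label trial, the descriptive comparison may be biased against Arm 1 for low-grade, non-serious events. To say that it is biased would go beyond the documents.

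The size cannot be derived. The 2-5 points rest on three assumptions: a 10% true risk in both arms, complete capture in Arm 1, and 50-80% capture in BSC. A lower risk or better BSC capture shrinks the figure, and equal capture brings it to zero.

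Two further inconsistencies add uncertainty about BSC recording. Protocol 8.1.5 and 8.6.7 pull in different directions on ECG findings, and SAP 3.2.1 starts AE reporting at an event that BSC subjects never have, contrary to Protocol 8.6.2. The correction is worth making because it is cheap and protects a primary safety objective.

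**What to change.** 1. State in Protocol 8.6.12 and 8.6.7 that ventricular arrhythmias are recorded on the AE eCRF page in both arms, from randomization to the end of the AE reporting period, irrespective of seriousness or causality.
2. Reconcile Protocol 8.1.5 with 8.6.7 so that one rule governs when an ECG finding becomes an AE, and say what the treatment period means for BSC subjects there and in SAP 3.2.4.
3. Align the start of AE reporting in SAP 3.2.1 with Protocol 8.6.2.

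Expedited reporting to the sponsor can remain a separate pharmacovigilance step for acalabrutinib recipients. Extending it to BSC would add work without changing any count.

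The cost is a few sentences across the two documents and a few more AE forms from BSC subjects. No additional tests are needed.
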